# JHM IRB - eForm A – Protocol

# 1. Abstract

The proposed research is a triple-blind, placebo–controlled, randomized clinical trial to evaluate the safety, efficacy and opiate-sparing effect of standard of care opiate (fentanyl) augmented with low-dose, slowly infused ketamine for the treatment of pain during acute burn wound care (e.g., twice-daily dressing changes). The standard of care for wound care among adults with acute intermediate and/or deep partial thickness burns involves twice daily wound care. Each wound care sessions, especially during the first week, involves severe pain during dressing removal, debridement, wound cleansing, re-application of topical ointment, and dressing replacement. The standard method for alleviating pain during wound care procedures is through the use of intravenous opiate medications (i.e., fentanyl).

Ketamine has recently emerged as a potentially effective analgesic alternative to narcotics for use in combat associated casualties. Early case reports, post hoc chart reviews and, more recently, small RCTs have consistently shown ketamine to be equal to or, more often, superior to opiate analgesics for treating acute pain in U.S. emergency departments and in combat casualties. There is an urgent need for a wellcontrolled and rigorously designed study with sufficient power to definitively test the hypothesis that fentanyl when augmented with low-dose, slow-infusion ketamine provides superior analgesia in the acute burn setting. Findings from acute burn centers are likely to generalize to a number of acute trauma settings, including injuries sustained in a battlefield setting.

We propose to enroll 94-104 acute adult burn patients hospitalized in the Johns Hopkins Bayview Medical Center's Johns Hopkins Burn Center (Burn Intensive Care Unit) who have sustained burns  $\geq 2\%$  and  $\leq 40\%$  total body surface area (TBSA  $\geq 2\%$  &  $\leq 40\%$ ). Subjects will be randomized to either a fentanyl + saline ("usual care" - UC) condition, or to fentanyl plus ketamine (K + UC) condition. Subjects in the K + UC condition will receive low-dose, slow-infusion ketamine using methodology previously employed in the small clinical trials reviewed in background section (see information below on medications, dosing, timing etc.). Subjects in the UC condition will receive fentanyl plus normal saline whereas those in the study drug arm will receive fentanyl plus ketamine. It is hypothesized that subjects in the K + UC condition will have superior pain relief with reductions in primary and secondary hyperalgesia, as well as reductions in allodynia. It is also hypothesized that adjunctive ketamine will be associated with an opiate sparing effect, reductions in symptoms of acute stress disorder, posttraumatic stress disorder, major depressive disorder and sleep disturbance during the study and for up to one month follow-up in the acute post-burn period.

b. DOSING -

# KETAMINE GROUP (Study Drug, Fentanyl PLUS Ketamine, slow infusion):

- i. Ketamine Loading Dose (Study Drug, slow infusion via programmed pump): 0.3 mg/kg, initiated approximately 10 minutes prior to wound care and infused over approximately 5 minutes... *THEN*
- ii. \*Fentanyl Loading Dose via programmed pump = 1 mcg / kg
- \*This is given to participants in both Group 1 and Group 2 starting at <1 minute before wound care.
- iii. Ketamine (Study Drug, Infusion via programmed pump): 2.5 mcg/kg/min, initiated immediately following the Fentanyl Loading Dose and continued for the duration of the session. The EPIC order set specifies that the nurse determines when the session is over, and that the nurse will turn off the infusion at that point.

# USUAL CARE GROUP (Fentanyl PLUS Saline)

- i. Saline Loading Dose (Placebo, Infusion via programmed pump) = An identical volume of saline as that in 0.3 mg/kg of ketamine. This will be initiated in the Usual Care group approximately 10 minutes before the wound care is set to begin and infused over approximately 5 minutes (i.e., during the same time that the Ketamine Group receives the ketamine loading dose).
- ii. \*Fentanyl (UC, injection via programmed pump) = 1 mcg / kg IV.
- \*This is given to participants in both Group 1 and Group 2 initiated < 1 minute prior to wound care.

  ii. Saline (Placebo, Infusion via programmed pump) = identical volume of fluid as that in 2.5 mcg/kg/min of ketamine, initiated immediately following the Loading Dose and continued for the duration of the session. . The EPIC order set specifies that the nurse determines when the session is over, and that the nurse will turn off the infusion at that point.

#### **PRN DOSE\***

i. PRN Fentanyl PRN (UC, injection) = 1 mcg / kg.

\*The PRN is provided to participants in both Group 1 and Group 2 when a participant requires additional pain medication. The criteria for providing PRN fentanyl are based on customary nursing practices, including a self-reported persistent rise in NAS pain  $\geq$ 2 or a NAS  $\geq$  7/10 (JCAHO standard) and combined with nursing judgment.

# 2. **Objectives**

There are two primary objectives and seven secondary objectives for this proposal. Primary objectives (i.e., Specific Aims #1 and #2) are:

# Specific Aim #1: To test the effectiveness of ketamine augmentation to usual care (fentanyl) (K+UC) relative to Usual Care (UC) in reducing the severity of acute nociceptive pain in response to pressure at: a) the burn wound (primary hyperalgesia); b) in body areas adjacent to the burn (secondary hyperalgesia) and; c) body areas distal to the burn (allodynia).

The standard of care for wound care procedures among adults with acute intermediate and/or deep burns involves twice daily wound care procedures. Each wound care procedure, especially during the first week, involves moderate to severe pain during dressing removal, debridement, wound cleansing, reapplication of topical ointment, and dressing replacement.

To compare and contrast the K+UC condition relative to the UC condition for reducing acute nociceptive pain, we will measure the following: 1) Self-reported pain and pain unpleasantness; 2) Sympathetic arousal; 3) Time until maximal pain relief; 4) Post-procedure, self-rated recall of average pain and pain unpleasantness following each wound care procedure, and self-rated satisfaction with pain management. Each of these is described below.

1) **Self-reported pain:** Pain is operationally defined as participant self-reported pain severity at the time of assessment, using the Numeric Analogue Scale (NAS) (McCaffrey, Pasero, 1999). NAS

Assessments will be performed within 5 minutes prior to administration of K+UC or UC, at the onset of the wound care procedure, every 10 minutes during each procedure, and at 15, 30, 45 and 60 minutes after the first and second procedures of the day, and, again at 6-hours post-procedure for the 1st wound care session each day.

The protocol standardizes body surface areas (wound, proximal, distal) where pain will be measured in the context of standardized pressure, and the duration and interval before releasing pressure. That is, pressure will be applied to each area, in turn, using standard force and a single fingertip, as when assessing skin blanching. This will be repeated once at each body location (wound, proximal, distal) assessed at the 30 minutes and 1-hour assessments during the first sessions on Day 1 (Session 1), Day 3 (Session 1), Day 5 (Session 1) and Day 7 (Session 1) and again at 1 hour after each of these wound care sessions is completed.

**Central Sensitization** - The NAS will be rated in regards to each of the following 3 patientspecific areas at each specified time point: a) Within the wound area (primary hyperalgesia); b) Skin proximal to but outside the wound area (secondary hyperalgesia) and c) Generalized pain at skin distal from the wound (allodynia). The repeated assessment of pain severity during the wound care will allow for evaluating increased pain hypersensitivity (hyperalgesia), and the assessment of pain for 1 hour afterwards will enable us to detect enhanced temporal summation of pain as has been observed among combat veterans with PTSD relative to combat veterans without PTSD and non-service members without PTSD (see below, Moeller-Bertram, Strigo, et al., 2016)

2) **Sympathetic arousal:** This will be measured using an Itamar Watch-PAT 200. This is a device that will be worn by all subjects while in the burn unit. In addition to providing measures of sympathetic reactivity prior to, during and after wound care, this device will also provide measures of sleep. A description of this device is provided at: https://www.youtube.com/watch?v=wE4pVhvS5Xg

3) Time to maximal pain relief and duration of time at maximal pain relief: These are operationally defined as: time elapsed between the start of wound care and the time at which the lowest pain rating is reported by each participant for each wound care session, and, the number of 10-minute observations where pain is reported at that maximal relief pain score. Thus, the NAS ratings will be used to create change scores (each NAS score subtracted from baseline score) with the largest change from baseline score designated as maximal pain relief. If the maximal pain relief is reflected in more than one rating, the first of these will represent the time to maximal pain relief.

4) **Recall Effect on Pain and Satisfaction With Pain Management:** This is defined as patient recall of average pain, and rating of satisfaction with wound care pain management. Recall of the average pain experienced during each of the 14 procedures will be rated 1-hour after each wound care sessions ends, and 6 hours afterward each AM session ends measured with the same 0-10 point NAS used to rate pain during the wound care procedure. This will allow testing of the well-documented memory effect whereby the worst and the last pain ratings during the procedure will best predict memory for pain afterwards.

Rating of satisfaction with wound care pain management will be measured using a numeric analog scale (ratings 1 to 100, with 1 = totally dissatisfied, and 100 = totally satisfied) at after each wound care sessions ends, and 6 hours afterward each AM session ends. Patient satisfaction is anticipated to be an inverse function of remembered pain, thus, it is expected that it will be inversely related to pain recall, and that the K+UC group will have higher satisfaction with pain management.

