# PRN DOSE (Fentanyl)\*

# PRN Fentanyl PRN (UC, injection) = 1 mcg / kg.

\*The PRN is provided to participants in both Group 1 and Group 2 when a participant requires additional pain medication. The criteria for providing PRN fentanyl are described next:

\*PRN – Standard of Care: Pain Severity for PRN Administration: The PRN is provided to participants in either Group 1 or Group 2 when a participant requires additional pain medication. In this protocol, the nurse will consider providing PRN fentanyl, if the participant's self-reported absolute pain severity is  $\geq$ 7/10 (JCAHO), **OR**, there is a persistent rise in pain severity that is  $\geq$ 2/10 above the most recent NAS rating. This protocol for providing PRN fentanyl takes into consideration both the standard nursing practice (i.e., persistent rise in pain severity  $\geq$ 2/10) as well as the JCAHO-standard cutoff for treating pain severity (i.e.,  $\geq$ 7/10).

\*PRN – Limit before Alternative Approaches are Considered: After each PRN fentanyl injection, no further PRN fentanyl should be given for at least 15minutes to allow time for the medication to have its effect and to prevent over-medication. It is recommended that consideration of alternative approaches be undertaken after 3 PRN fentanyl injections (i.e., three injections of "1 mcg / kg of PRN fentanyl") as described below. It is also recommended that if there is a failure to reduce pain intensity by  $\geq$  2/10 after at least 15minutes after PRN administration, another PRN or alternative medication be considered.

The maximum number of PRN fentanyl administrations as well as any alternative approaches will be decided at the discretion of the wound care nurse and the provider on the basis of their Best Care Practices and the consideration of each specific participant's circumstances.

\*PRN – Nursing / Provider Judgment: Furthermore, when determining the patient's need for additional analgesic or alternative medication, the trained and experienced BICU nurse and provider often employ assessment of factors other than self-reported pain intensity. These additional factors will also be utilized by the wound care nurse and provider in deciding what medication is or is not necessary during this "Ketamine for Acute Pain During Burn Wound Care" protocol.

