#### 1. Sample Size Estimate Based on Stay $\geq$ 7 days in Burn ICU.

The sample size calculation is based on the primary statistical procedure for this project which will test the difference in mean pain scores, defined as the average self-report of mean pain score, based on the Numeric Analogue Scale (NAS), during each burn wound care procedures, between individuals randomized to usual care plus placebo (fentanyl plus saline) and those randomized to the intervention arm (usual care + ketamine). PASS Sample Size (Version 14) was used to perform all sample size calculations while considering individuals over the one-year study duration randomized to control and intervention arms in a 1:1 fashion.

In the first case, we further assume that each individual, will, on average, have a length of stay of 7 days thus resulting in 14 wound care procedures performed during hospital stay. We determined the minimum sample size for our trial based on 80% power at p = 0.05 to detect a clinically significant difference in mean pain score during the wound care procedure of 2.0 points between the control and intervention arms with a standard deviation of 3.0. In addition, to account for the clustered nature of procedures performed on individuals, we have used a sample size inflator (also termed "design effect") of 10.1 as described by the Cochrane manual@ conservatively using an interclass correlation of effects of 0.7 amongst repeated measures of pain scores within each individual and 14 observations per individual.

The required sample size needed to accept the alternative hypotheses that the mean pain care score in the intervention arm decreased by 2 points compared to the control arm at the 0.05 level would require 27 individuals per arm (54 total), our anticipated population of 74 eligible individuals is adequate to show a clinically significant improvement for both intervention arms.

@http://handbook.cochrane.org/chapter\_16/16\_3\_4\_approximate\_analyses\_of\_cluster\_randomized\_trials\_for\_a.htm

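### Time to maximal pain relief needs no relief to occur: within the procedure, flat or steadily rising pain scores 0 minutes, so the measure can run opposite to benefit

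*Combined protocol and SAP*

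**What the plan says.** Specific Aim #1 lists four measures of acute pain. The third, time to maximal pain relief, is the "time elapsed between the start of wound care and the time at which the lowest pain rating is reported by each participant", for each session. Change scores are formed with "each NAS score subtracted from baseline score", and the largest is designated maximal relief. For ties: "If the maximal pain relief is reflected in more than one rating, the first of these will represent the time to maximal pain relief". A companion duration measure is "the number of 10-minute observations where pain is reported at that maximal relief pain score".

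Measure 1 of the same aim schedules a NAS within 5 minutes before study drug, then "at the onset of the wound care procedure, every 10 minutes during each procedure, and at 15, 30, 45 and 60 minutes after" the procedure, with a further 6-hour rating after the first session of the day. Study drug starts about 10 minutes before wound care (Abstract, dosing), so relief can already be present at time 0.

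The Background treats a shorter time as a possible distinct advantage of ketamine, citing an emergency-department trial with 5 minutes for ketamine and 100 for morphine.

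The plan sets no minimum change and no not-attained or censoring rule for this measure. Measure 3 does not say which rating is baseline or whether post-procedure ratings count.

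**The concern.** A time-to-relief measure should give its best score to early relief and its worst to none. This rule dates the lowest rating, however high that rating is. A session without relief still receives a time, and if pain starts at its lowest and stays there or rises, that time is the best possible.

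If the arms differ in slope or in the share of sessions without relief, the arm with more benefit can look slower. If one arm is simply lower throughout, the measure can miss it. Either result could be read as evidence on the speed advantage that the Background hopes to replicate.

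**Working it through.** The plan gives no effect size, power or sample size for this measure, so there is no stated figure to reproduce. The check applies the rule as written.

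**Rule.** With baseline B and ratings y_j at times t_j, c_j = B − y_j and M = max c_j. Time is the first t_j with c_j = M; duration is the number of ratings with c_j = M. B is constant within a session, so the largest c_j is always the smallest y_j. Baseline therefore drops out of the time score, and only the shape of the profile matters.

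**Worked sessions** (assumed ratings at 0, 10, 20, 30 and 40 minutes, in-procedure only):

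| Baseline | Ratings | M | Time (min) | Duration |
|---|---|---|---|---|
| 9 | 9,9,9,9,9 | 0 | 0 | 5 of 5 |
| 5 | 6,7,8,9,9 | −1 | 0 | 1 of 5 |
| 8 | 2,3,3,3,3 | 6 | 0 | 1 of 5 |
| 8 | 8,6,4,3,2 | 6 | 40 | 1 of 5 |
| 8 | 9,9,9,8,8 | 0 | 30 | 2 of 5 |

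The last row shows that not every no-relief session scores early.

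**Simple arm comparison** (assumed). All ketamine sessions reach relief at 20 minutes, usual-care responders at 30, and a fraction f of usual-care sessions has flat or rising pain and scores 0. The usual-care mean is 30(1 − f): 30, 22.5, 15 and 7.5 minutes at f = 0, 0.25, 0.5 and 0.75. It falls below 20 once f exceeds 1/3.

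**Simulation** (all inputs assumed). NAS = 7 + slope × (number of 10-minute steps) + patient effect (SD 1.5) + rating error (SD 1.2), rounded and clipped to 0–10. Pre-drug mean is 7; 100,000 sessions per slope. The last two rows score the measure proposed below on the same sessions.

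| Slope per 10 min | +0.5 | 0 | −0.5 | −1.0 |
|---|---|---|---|---|
| Mean time as written (min) | 6.3 | 15.1 | 26.5 | 33.2 |
| Scored 0 min | 60% | 32% | 8% | 1% |
| Mean duration (of 5) | 1.55 | 1.60 | 1.46 | 1.31 |
| Attained, proposed measure | 28% | 46% | 78% | 97% |
| Mean time, proposed (not attained = 50 min) | 37.6 | 32.9 | 25.1 | 18.5 |

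With rating error SD 0.8 to 1.6, mean times as written are 3–9, 13–16, 25–29 and 31–35 minutes.

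**Arms that mix responders and non-responders.** With 70% v 30% of sessions improving by 1.0 per 10 minutes and the rest flat, the rule gives 27.8 v 20.6 minutes, although mean NAS is 5.58 v 6.37. The proposed measure is attained in 81% v 61%.

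**Parallel arms.** Mean profiles 3,5,5,5,4 v 5,7,7,7,6 with pre-drug mean 6 give 8.0 v 8.1 minutes as written. The proposed measure is attained in 89% v 47%.

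**If post-procedure ratings count.** With ratings at 55, 70, 85 and 100 minutes and assumed means of 5,4,4,4 after flat pain and 3,3,3,3 after improving pain, mean times are 76 (flat) v 57 (improving), which is not reversed. Pain that stays exactly flat through those ratings still scores 0.

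**The case against.** - **Noise.** Real ratings fluctuate. Only 32% of simulated flat sessions and 60% of rising ones score exactly 0, and mean duration hardly varies with slope. This stands for the clean examples. The ordering of mean times is still reversed.
- **Reading.** If post-procedure ratings count, the assumed example is not reversed. This stands, and the conclusion is limited accordingly. That the direction turns on an unstated choice is itself a reason to change the text.
- **PRN fentanyl.** It is considered at NAS 7 or above, or after a persistent rise of 2 or more, so sustained high or rising pain should be less common than the examples suggest. It can be declined, and flat pain below 7 does not trigger it. The simulation has no PRN effect.
- **Inputs.** The assumed total SD is √(1.5² + 1.2²) = 1.92 and the ICC is 2.25/3.69 = 0.61, whereas the first sample size calculation uses 3.0 and 0.7. Applying those two values to individual ratings (itself an assumption) gives 8, 16, 24 and 30 minutes: same direction, smaller gradient.
- **Smaller remedy.** One could keep the measure, name the eligible ratings and the baseline, and mark sessions with no positive change as not attained. With pre-drug mean 7 and such sessions set to 50 minutes, the better arm is still slower in the 70% v 30% mix (31.1 v 27.9). At pre-drug means of 5 and 3 this reversal disappears, so the remedy works only in some settings.
- **Weight.** No test or power is attached to this measure, and longitudinal and trajectory analyses are planned. This limits the consequence.

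**Conclusion.** The concern holds. The rule contains no relief condition, and an onset rating is scheduled. On the in-procedure reading it therefore gives 0 minutes to flat and steadily rising pain, the same as to relief present at onset. This follows from the text and needs no simulation.

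The size at arm level rests on assumed profiles and variances. The better arm appears about 7 minutes slower (27.8 − 20.6 = 7.2) in the 70% v 30% mix, and a constant 2-point benefit is missed. Reversal is possible rather than certain, and it depends on the unstated role of the post-procedure ratings.

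The defect should be corrected, but it does not reach the sample size. The "primary statistical procedure for this project which will test the difference in mean pain scores" uses mean NAS and is unaffected.

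**What to change.** Define the measure as time from start of wound care to the first in-procedure rating at least 2 points below the NAS taken within 5 minutes before study drug. In addition:

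- State that the 15- to 60-minute post-procedure ratings are not used.
- Count relief present at onset as attained at time 0. Record sessions that never reach the threshold as not attained, either at worst rank or censored at the last in-procedure rating.
- Analyse with a rank-based or discrete-time model that allows for clustering within patient.
- Report sessions with pre-drug NAS below 2 separately, since they cannot attain.
- Replace duration with the proportion of in-procedure ratings at least 2 points below pre-drug NAS (8%, 18%, 39% and 58% across the four simulated slopes), and report the size of maximal relief alongside.
- Give a worst-rank sensitivity analysis. "The EPIC order set specifies that the nurse determines when the session is over", and session end and PRN fentanyl may both be related to pain, so censoring may be informative.

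The 2-point threshold is a choice made for scoring only. The PRN section uses the same margin, where it reconsiders treatment "if there is a failure to reduce pain intensity by" at least 2/10.

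**Cost.** Outcome wording and scoring code; the ratings are already collected. There are three downsides:

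- The measure departs from the literal maximum-relief construct in the Background.
- Single-rating noise lets 46% of flat and 28% of worsening simulated sessions attain.
- Attainment falls when pre-drug pain is low. In the 70% v 30% mix it is 51% v 26% at a pre-drug mean of 5 and 15% v 7% at a mean of 3, with the arms still in the right order. The share that cannot attain is 0.2%, 3% and 22% at pre-drug means of 7, 5 and 3.
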